#### 12. STATISTICAL CONSIDERATIONS

This is a phase II open-label single arm and single institution clinical trial to evaluate the efficacy and safety of CB-103 in combination with venetoclax in adolescent and adult patients with T-ALL/T-LL in first or second bone marrow recurrence refractory to initial induction therapy or refractory to at least one reinduction attempt. Up to 30 patients may be enrolled, without regard to Notch status; we anticipate that approximately 50% of these patients will be Notch positive. The primary efficacy endpoint of the study is overall response rate (ORR, including CR,CRi and PR rate) after the first two induction cycles, and the primary toxicity endpoint is the rate of toxic events, defined as a grade ≥3 non-haemtological AEs that are possibly or probably related to the study drugs (see Adverse Events (SAE) definition in section 9.2.2.1.) occurring during the 28 days of induction cycle.

We simultaneously monitor efficacy and toxicity using the Bayesian optimal phase 2 (BOP2) design [32]. Specifically, let n denote the interim sample size, and N denote the maximum sample size. Let  $Y_{eff}$  and  $Y_{tox}$  denote the binary efficacy and toxicity endpoints, with  $Y_{eff} = 1$  and  $Y_{tox} = 1$  indicating that patients experience efficacy and toxicity, respectively. We assume that the joint distribution of  $(Y_{eff}, Y_{tox})$  follows a multinomial distribution with four elementary outcomes:  $(Y_{eff}, Y_{tox}) = (1, 1), (1, 0), (0, 1)$  and (0, 0). Let  $\mathbf{p} = (P_{11}, P_{10}, P_{01}, P_{00})$  denote the probabilities of observing the four outcomes, and let  $P_{eff} = Pr(Y_{eff} = 1), P_{tox} = Pr(Y_{tox} = 1)$  and  $P_{efftox} = Pr(Y_{eff} = 1, Y_{tox} = 1)$ . When efficacy and toxicity endpoints are monitored separately, the joint distribution reduced to marginal distribution of efficacy and marginal distribution of toxicity, respectively.

The treatment is deemed unacceptable if  $p_{eff} \le 0.15$  or  $p_{tox} > 0.20$ . Thus, we will stop enrolling patients and claim that the treatment is unacceptable if

$$Pr(p_{eff} > 0.15|data) < \lambda \left(\frac{n}{N}\right)^{\alpha}$$

or

$$Pr(p_{tox} \le 0.20|data) < \lambda \left(\frac{n}{N}\right)^{\alpha/3},$$

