where  $\lambda$ =0.57 and  $\alpha$ =0.86 are design parameters optimized to maximize the study power, i.e., probability of correctly concluding an efficacious and safe **treatment as acceptable** when  $p_{eff}=0.3$ ,  $p_{tox}=0.10$  and  $p_{efftox}=0.05$ , while controlling that the probability of incorrectly claiming an inefficacious and toxic treatment, i.e., type I error, with  $p_{eff}=0.15$ ,  $p_{tox}=0.20$  and  $p_{efftox}=0.05$ , to 8.3%. Note that in the safety stopping rule, the original publication of the design used the probability cutoff  $\lambda(n/N)^{\alpha}$ , here the attenuation factor 3 is added (i.e.,  $\alpha/3$ ) to obtain stricter interim stopping boundaries to enhance safety.

This optimization is performed assuming a vague Dirichlet prior Dir(0.05,0.1,0.15,0.7) for p. The prior is chosen such that it corresponds to a prior effective sample size of 1 patient, and the prior estimates of p\_eff and p\_tox match the values specified when the treatment is unacceptable. The above decision rule leads to the following optimal stopping boundaries:

Table 18: Optimized stopping boundaries

# patients treate	d Stop if # response <=	OR # toxicity >=
10	0	3
20	2	5
30	5	6

When the total number of patients reaches the maximum sample size of 30, we conclude that the treatment is acceptable if the number of responses are greater than 5, and the number of toxicities are less than 6; otherwise we conclude that the treatment is unacceptable. The go/no-go criteria in Table 18 are non-binding.

Below (**Table 19**) are the operating characteristics of the design based on 10000 simulations using the BOP2 web application (BOP2 V1.4.10.0), which is available at http://www.trialdesign.org.

Table 19: Operating characteristics

Scenario	Pr(Eff)	Pr(Tox)	Pr(Eff & Tox)	Early Stopping (%)	Claim Acceptable (%)	Average Sample Size
1	0.30	0.2	0.05	48.77	33.34	21.7
2	0.15	0.3	0.05	89.47	1.56	14.2
3	0.30	0.1	0.05	14.26	77.76	27.6
4	0.15	0.1	0.05	51.07	20.83	22.3
5	0.30	0.2	0.10	49.39	31.94	21.6
6	0.15	0.2	0.05	71.48	8.34	18.2
7	0.20	0.1	0.05	31.75	45.19	25.1
8	0.15	0.4	0.06	97.62	0.19	11.6
9	0.40	0.1	0.06	9.74	86.76	28.3
10	0.40	0.4	0.16	96.03	0.50	12.1

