25/30     0.83 (0.66, 0.93)       26/30     0.87 (0.7, 0.95)       27/30     0.9 (0.74, 0.97)       28/30     0.93 (0.78, 0.99)       29/30     0.97 (0.82, 1)	23/30	0.77 (0.59, 0.88)
26/30     0.87 (0.7, 0.95)       27/30     0.9 (0.74, 0.97)       28/30     0.93 (0.78, 0.99)       29/30     0.97 (0.82, 1)	24/30	0.8 (0.62, 0.91)
27/30     0.9 (0.74, 0.97)       28/30     0.93 (0.78, 0.99)       29/30     0.97 (0.82, 1)	25/30	0.83 (0.66, 0.93)
28/30 0.93 (0.78, 0.99) 29/30 0.97 (0.82, 1)	26/30	0.87 (0.7, 0.95)
29/30 0.97 (0.82, 1)	27/30	0.9 (0.74, 0.97)
	28/30	0.93 (0.78, 0.99)
30/30 1 (0.87, 1)	29/30	0.97 (0.82, 1)
	30/30	1 (0.87, 1)

In secondary analysis, ORR will be summarized separately by Notch status as proportions with corresponding 95% Agresti-Coull confidence intervals. The difference in ORR between Notch groups will be assessed by Fisher's exact test.

Other measures of response (CR, Cri, PR, relapse, radiographic tumor response, CNS remission, CNS relapse) and minimal residual disease (MRD) will be summarized as proportions with corresponding 95% Agresti-Coull confidence intervals.

Duration of Response (DoR), Overall Survival (OS), and event-free Survival (EFS) will be summarized using Kaplan-Meier methods.

In exploratory analyses, correlations between ORR and pharmacokinetic and pharmacodynamics markers will be summarized. Rates of patients transitioning to Hematopoietic stem cell transplant (HSCT) will be summarized. Endpoints may be further summarized separately by Notch status.

Additional statistical methods may be used.

The Investigator is responsible for completing an efficacy/safety summary reports and submitting it to the IND Office Medical Affairs and Safety Group, for review and approval.

This should be submitted after the first 10 evaluable patients complete 1 cycle of study treatment, and every 10 evaluable patients, thereafter. Efficacy summary will be submitted for every 10 evaluable patients after they complete 2 cycles of therapy.

Page | 52 04/25/2024

A copy of the safety summary report should be placed in the Investigator's Regulatory Binder under "sponsor correspondence".

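### Cheap improvement: when the running toxicity count reaches the next Table 18 boundary, Section 12 should pause enrolment and call for a report then, instead of leaving both to the next 10-patient review

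*Combined protocol and SAP*

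**What the plan says.** Section 12 describes a BOP2 design with a ceiling of 30 patients ("Up to 30 patients may be enrolled, without regard to Notch status"). The toxicity endpoint is a grade 3 or higher non-haematological adverse event, possibly or probably related to the study drugs, "occurring during the 28 days of induction cycle".

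The monitoring rule reads "we will stop enrolling patients and claim that the treatment is unacceptable if", followed by one posterior inequality for efficacy and one for toxicity. Table 18 turns these into counts at 10, 20 and 30 patients. The toxicity stops are at least 3, 5 and 6; the response stops are at most 0, 2 and 5. At 30 patients the treatment is acceptable "if the number of responses are greater than 5, and the number of toxicities are less than 6". Section 12 also says that the toxicity cutoff was tightened (exponent α/3) for the sake of safety, and that the Table 18 criteria are non-binding.

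On timing, the safety summary is due as follows: "This should be submitted after the first 10 evaluable patients complete 1 cycle of study treatment, and every 10 evaluable patients, thereafter". The efficacy summary is due for every 10 evaluable patients after two cycles.

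Other safety routes run throughout the trial: SAE reporting (Sections 9.2.2.2 and 9.2.2.3) and the investigators' right to terminate (Section 10.5). Neither refers to the Table 18 count.

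**The concern.** Suppose three of the first six patients have a qualifying toxicity. Whatever happens to patients 7 to 10, the count at 10 will be at least 3, so the first boundary will be crossed. The only step in the plan that depends on the count is still the summary due after ten evaluable patients complete cycle 1. Up to seven more patients could be treated under a rule whose result is already known. The same gap exists before the second look (fifth event before patient 20) and before the final analysis (sixth event before patient 30).

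The stake is patient exposure, and it grows with the true toxicity rate. The validity of the test is not at stake.

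**Working it through.** **Inputs (all Section 12).** N = 30; λ = 0.57 and α = 0.86, which "are design parameters optimized to maximize the study power"; limits of 0.15 (efficacy) and 0.20 (toxicity); the prior ("This optimization is performed assuming a vague Dirichlet prior Dir(0.05,0.1,0.15,0.7) for p"); the Table 18 counts; the ten Table 19 scenarios.

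**Step 1: reproduce Table 18.** The Dirichlet prior gives marginals Beta(0.15, 0.85) for efficacy and Beta(0.20, 0.80) for toxicity. Stop for toxicity when Pr(p_tox ≤ 0.20 | x of n) < 0.57(n/30)^(0.86/3). The cutoffs are 0.416, 0.5075 and 0.570 at n = 10, 20 and 30. At n = 10, two events give a posterior of 0.561 (continue) and three give 0.272 (stop). All six counts in Table 18 reproduce.

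**Step 2: reproduce Table 19.** An exact recursion over (responses, toxicities) with looks at 10, 20 and 30 gives:
- scenario 6: 8.17% acceptable (Table 19: 8.34%)
- scenario 3: 78.46% acceptable (Table 19: 77.76%)

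The simulation standard errors are √(0.0834 × 0.9166/10000) = 0.28 points and √(0.7776 × 0.2224/10000) = 0.42 points, so the gaps are 0.6 and 1.7 standard errors. Every row agrees within 0.71 points and 0.11 patients.

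**Step 3: how often the first count is reached early.** The third toxicity falls at patient j with probability C(j−1, 2) p³(1−p)^(j−3). Summing over j = 3 to 10 gives the chance of crossing at the first look; j = 3 to 9 gives the chance that it is already settled before patient 10.

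| p_tox | P(≥3 of 10) | P(third before patient 10) | Mean position of third, given crossing | Mean patients after it, given crossing |
|---|---|---|---|---|
| 0.10 | 7.0% | 5.3% | 7.9 | 2.1 |
| 0.20 | 32.2% | 26.2% | 7.5 | 2.5 |
| 0.30 | 61.7% | 53.7% | 7.0 | 3.0 |
| 0.40 | 83.3% | 76.8% | 6.3 | 3.7 |

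**Step 4: act when the count is reached.** If the count is at least 3 at some j ≤ 10, it is at least 3 at 10; likewise 5 by 20 and 6 by 30. The trials stopped early are exactly those that the scheduled toxicity rule would have failed. The acceptance probability therefore cannot change, and the recursion confirms this in all ten scenarios. Mean patients treated (exact):

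| Scenario | p_eff, p_tox | Acceptable, both ways | Planned | Early action before looks 1 and 2 | Also before the final analysis |
|---|---|---|---|---|---|
| 8 | 0.15, 0.40 | 0.12% | 11.56 | 8.17 | 8.07 |
| 2 | 0.15, 0.30 | 1.56% | 14.09 | 11.80 | 11.52 |
| 6 | 0.15, 0.20 | 8.17% | 18.14 | 17.10 | 16.79 |
| 3 | 0.30, 0.10 | 78.46% | 27.63 | 27.45 | 27.37 |

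**Step 5: allow for overlap.** The figures above assume that each outcome is known before the next enrolment. The accrual rate is not given. As an assumption, let k further patients enter before the deciding event is known, with enrolment held at each look, so that min(j + k, next look) patients are treated. For k = 0, 1, 2 and 3 the mean saving is:
- scenario 8: 11.56 minus 8.07, 8.95, 9.74 and 10.40, or 3.5, 2.6, 1.8 and 1.2 patients
- scenario 6: 18.14 minus 16.79, 17.22, 17.55 and 17.80, or 1.3, 0.9, 0.6 and 0.3 patients

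The acceptance probability is unaffected by k.

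**The case against.** Looks every 10 patients are a disclosed design choice, with operating characteristics in Table 19 that reproduce. There is no error or contradiction here.

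A reader might infer that the third toxicity fixes the decision to stop. The documents do not support that. The criteria are non-binding, so the event fixes a boundary crossing and the sponsor still decides. The statement that acceptance is unchanged holds for the rule as simulated, that is, with the criteria followed.

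A reader might also infer that the plan bars action between looks. It does not. The quoted sentence sets when a report is due, and SAE reporting and the right to terminate operate throughout. These make extra exposure less certain but do not close the gap: they are not tied to the count, and a related grade 3 event need not meet the seriousness criteria in Section 9.2.2.2.

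Nor is waiting wholly without value. Patients treated up to the look add to the ORR and toxicity estimates and their confidence intervals. This weighs most against early action on the sixth toxicity, where Table 18 is judging acceptability and a pause would mainly truncate the efficacy data.

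Finally, the saving is best case, and at the 10% toxicity rate for which the design is powered it is only about 0.3 patients (27.63 − 27.37). All of this stands and limits the size of the point. None of it is a reason to leave a reached count without a linked action.

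**Conclusion.** The point holds as a cheap safety improvement. It does not show an invalid design. Table 18 counts can be reached before the scheduled look, and the plan attaches no pause or report to that event. If the criteria are followed, acting on it costs no power and does not alter the type I error.

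In the best case it spares about 3.5 patients on average at 40% toxicity, 2.6 at 30%, 1.3 at the joint null and 0.3 at 10%. Late ascertainment within the 28-day window could make these savings smaller; Step 5 shows how far under one assumption. Patients who might enter after the tenth while that patient completes cycle 1 are not counted, because neither an accrual rate nor an enrolment hold is stated.

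One further reading should be ruled out. Acting when a scheduled count is reached is not the same as applying the posterior inequality after every patient. That would stop at 1 toxicity for n = 1 or 2 and at 2 toxicities for n = 3 to 7. It would be a different design with different operating characteristics.

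**What to change.** Add to Section 12, in substance:

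- Enrolment is suspended and a safety summary is submitted as soon as the toxicity count for the next scheduled look in Table 18 is reached: the third qualifying toxicity among the first 10 patients, or the fifth among the first 20. The sixth among 30 may be added as an option.
- The sponsor then decides how to proceed, since the criteria are non-binding.
- The posterior inequality is still evaluated only at the scheduled looks.
- The efficacy looks are unchanged.

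Use one denominator throughout: Table 18 counts patients treated, while the reporting paragraph counts evaluable patients. Section 9 makes a patient evaluable for safety after one dose of CB-103 but evaluable for response only after more than half the CB-103 dose.

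The cost is a few sentences and a running tally of qualifying events. The acceptance column of Table 19 stands. The average sample sizes would be somewhat lower and should be rerun or footnoted. If the sixth-event option is adopted, the early-stopping column needs the same treatment. The price is slightly fewer patients in the descriptive ORR and toxicity estimates when the trial stops early.

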# **Appendix 1 QT Prolonging Drugs with Risk of Torsades de Pointes.**

**Table 1** List of prohibited QT prolonging drugs with a known risk to induce Torsades de Pointes

Drug	QT risk (*)	Comment
Aclarubicin	Known risk for TdP	Not available in US
Amiodarone	Known risk for TdP	Females >Males, TdP risk regarded as low
Anagrelide	Known risk for TdP	
Arsenic trioxide	Known risk for TdP	
Astemizole	Known risk for TdP	Removed from US market
Azithromycin	Known risk for TdP	Females>Males
Bepridil	Known risk for TdP	Removed from US market; Females>Males
Cesium chloride	Known risk for TdP	
Chloroquine	Known risk for TdP	
Chlorpromazine	Known risk for TdP	
Chlorprotixene	Known risk for TdP	Not available in US
Cilostazol	Known risk for TdP	
Ciprofloxacin	Known risk for TdP	
Cisapride	Known risk for TdP	Removed from US market; Females>Males
Citalopram	Known risk for TdP	
Clarithromycin	Known risk for TdP	
Cocaine	Known risk for TdP	
Disopyramide	Known risk for TdP	Females>Males
Dofetilide	Known risk for TdP	
Domperidone	Known risk for TdP	Not available in the US
Donepezil	Known risk for TdP	
Dronedarone	Known risk for TdP	
Droperidol	Known risk for TdP	
Erythromycin	Known risk for TdP	
Escitalopram	Known risk for TdP	
Flecainide	Known risk for TdP	
Fluconazole	Known risk for TdP	
Gatifloxacin	Known risk for TdP	Removed from US market
Grepafloxacin	Known risk for TdP	Removed from US market
Halofantrine	Known risk for TdP	Not available in US; Females>Males
		When given i.v. or at higher than
Haloperidol	Known risk for TdP	recommended doses, risk of sudden death,
·		QT prolongation and torsades increased
Hydroquinidine	Known risk for TdP	Not available in US
Hydroxychloroquin	Known rich for Tab	
е	Known risk for TdP	
Ibogaine	Known risk for TdP	Not available in US
Ibutilide	Known risk for TdP	Females>Males
Levofloxacin	Known risk for TdP	
Levomepromazine	Known risk for TdP	Not available in the US
Levomethadyl acetate	Known risk for TdP	Removed from US market

Drug	QT risk (*)	Comment
Levosulpiride	Known risk for TdP	Not available in US
Meglumine antimoniate	Known risk for TdP	Not available in US
Mesoridazine	Known risk for TdP	Removed from US market
Methadone	Known risk for TdP	Females>Males
Mobocertinib	Known risk for TdP	
Moxifloxacin	Known risk for TdP	
Nifekalant	Known risk for TdP	Not available in US
Ondansetron	Known risk for TdP	
Oxaliplatin	Known risk for TdP	
Papaverine HCl	Known risk for TdP	Intracoronary
Pentamidine	Known risk for TdP	Females>Males
Pimozide	Known risk for TdP	Females>Males
Probucol	Known risk for TdP	Removed from US market
Procainamide	Known risk for TdP	
Propofol	Known risk for TdP	
Quinidine	Known risk for TdP	Females>Males
Roxithromycin	Known risk for TdP	Not available in US
Sertindole	Known risk for TdP	Not available in US
Sevoflurane	Known risk for TdP	
Sotalol	Known risk for TdP	Females>Males
Sparfloxacin	Known risk for TdP	Removed from US market
Sulpiride	Known risk for TdP	Not available in US
Sultopride	Known risk for TdP	Not available in US
Terfenadine	Known risk for TdP	Removed from US market
Terlipressin	Known risk for TdP	Not available in US
Terodiline	Known risk for TdP	Not available in US
Thioridazine	Known risk for TdP	
Vandetanib	Known risk for TdP	

Source:

**Table 2** List of QT prolonging drugs with a conditional risk to induce Torsades de Pointes

Drug	QT risk (*)
Abiraterone	Conditional risk for TdP
Amantadine	Conditional risk for TdP
Amisulpride (not available in the US)	Conditional risk for TdP
Amitriptyline	Conditional risk for TdP
Amphotericin B	Conditional risk for TdP
Amsacrine (not available in the US)	Conditional risk for TdP
Atazanavir	Conditional risk for TdP
Bendroflumethiazide or bendrofluazide	Conditional risk for TdP
Chloral hydrate	Conditional risk for TdP

(\*) Classification according to the Qtdrugs org advisory board of the Arizona CET. Updated versions of medications which may prolong the QTc interval may be found at the following website: https://crediblemeds.org/index.php/?cID=328

Drug	QT risk (*)
Cimetidine	Conditional risk for TdP
Clofazimine	Conditional risk for TdP
Clomipramine	Conditional risk for TdP
Dilitazem	Conditional risk for TdP
Diphenhydramine	Conditional risk for TdP
Doxepin	Conditional risk for TdP
Eperisone (not available in the US)	Conditional risk for TdP
Esomeprazole	Conditional risk for TdP
Famotidine	Conditional risk for TdP
Fluoxetine	Conditional risk for TdP
Fluvoxamine	Conditional risk for TdP
Furosemide (frusemide)	Conditional risk for TdP
Galantamine	Conditional risk for TdP
Garenoxacin (not available in the US)	Conditional risk for TdP
Hydrochlorothiazide	Conditional risk for TdP
Hydroxyzine	Conditional risk for TdP
Indapamide	Conditional risk for TdP
Itraconazole	Conditional risk for TdP
Ivabradine	Conditional risk for TdP
Ketoconazole	Conditional risk for TdP
Lansoprazole	Conditional risk for TdP
Loperamide	Conditional risk for TdP
Metoclopramide	Conditional risk for TdP
Metolazone	Conditional risk for TdP
Metronidazole	Conditional risk for TdP
Nelfinavir	Conditional risk for TdP
Olanzapine	Conditional risk for TdP
Omeprazole	Conditional risk for TdP
Pantoprazole	Conditional risk for TdP
Paroxetine	Conditional risk for TdP
Piperacillin/Tazobactam	Conditional risk for TdP
Posaconazole	Conditional risk for TdP
Propafenone	Conditional risk for TdP
Quetiapine	Conditional risk for TdP
Quinine sulfate	Conditional risk for TdP
Ranolazine	Conditional risk for TdP
Risperidone	Conditional risk for TdP
Sertraline	Conditional risk for TdP
Solifenacin	Conditional risk for TdP
Telaprevir	Conditional risk for TdP
Torsemide (Torasemide)	Conditional risk for TdP
Trazodone	Conditional risk for TdP
Voriconazole	Conditional risk for TdP
Ziprasidone	Conditional risk for TdP
Source:	

#### Source

(\*) Classification according to the Qtdrugs org advisory board of the Arizona CET. Updated versions of medications which may prolong the QTc interval may be found at the following website: https://crediblemeds.org/index.php/?cID=328

**Table 3** List of QT prolonging drugs with a possible risk to induce Torsades de Pointes

Drug	QT risk (*)
Abarelix (not available in the US)	Possible risk for TdP
Alfuzosin	Possible risk for TdP
Alimemazine (not available in the US)	Possible risk for TdP
Apalutamide	Possible risk for TdP
Apomorphine	Possible risk for TdP
Aripiprazole	Possible risk for TdP
Artemether/Lumefantrine	Possible risk for TdP
Artenimol+piperaquine (not available in the US)	Possible risk for TdP
Asenapine	Possible risk for TdP
Atomoxetine	Possible risk for TdP
Bedaquiline	Possible risk for TdP
Bendamustine	Possible risk for TdP
Betrixaban	Possible risk for TdP
Bicalutamide	Possible risk for TdP
Bortezomib	Possible risk for TdP
Bosutinib	Possible risk for TdP
Buprenorphine	Possible risk for TdP
Cabozantinib	Possible risk for TdP
Capecitabine	Possible risk for TdP
Carbetocin	Possible risk for TdP
	Possible risk for TdP
Ceritinib	
Closaria a	Possible risk for TdP
Cobine	Possible risk for TdP
Cobimetinib	Possible risk for TdP
Crizotinib	Possible risk for TdP
Cyamemazine (not available in the US)	Possible risk for TdP
Dabrafenib	Possible risk for TdP
Dasatinib	Possible risk for TdP
Degarelix	Possible risk for TdP
Delamanid (not available in the US)	Possible risk for TdP
Desipramine	Possible risk for TdP
Deutetrabenazine	Possible risk for TdP
Dexmedetomidine	Possible risk for TdP
Dextromethorphan/Quinidine	Possible risk for TdP
Dolasetron	Possible risk for TdP
Efavirenz	Possible risk for TdP
Eliglustat	Possible risk for TdP
Encorafenib	Possible risk for TdP
Entrectinib	Possible risk for TdP
Epirubicin	Possible risk for TdP
Eribulin mesylate	Possible risk for TdP
Ezogabine (Retigabine)	Possible risk for TdP
Felbamate	Possible risk for TdP
Fingolimod	Possible risk for TdP

Drug	QT risk (*)
Fluorouracil (5-FU)	Possible risk for TdP
Flupentixol (not available in the US)	Possible risk for TdP
Gemifloxacin	Possible risk for TdP
Gilteritinib	Possible risk for TdP
Glasdegib	Possible risk for TdP
Granisetron	Possible risk for TdP
Hydrocodone - ER	Possible risk for TdP
lloperidone	Possible risk for TdP
Imatinib	Possible risk for TdP
Imipramine (melipramine)	Possible risk for TdP
Inotuzumab ozogamicin	Possible risk for TdP
Isradipine	Possible risk for TdP
Ivosidenib	Possible risk for TdP
Ketanserin (not available in the US)	Possible risk for TdP
Lacidipine (not available in the US)	Possible risk for TdP
Lapatinib	Possible risk for TdP
Lefamulin	Possible risk for TdP
Lenvatinib	Possible risk for TdP
Leuprolide	Possible risk for TdP
Levetiracetam	Possible risk for TdP
Levoketoconazole	1 033IDIC 113K TOT TUT
Levomethadone (not available in the US)	Possible risk for TdP
Lithium	Possible risk for TdP
Lofexidine	Possible risk for TdP
Lopinavir/Ritonavir	Possible risk for TdP
Lumateperone	Possible risk for TdP
Lurasidone	Possible risk for TdP
Maprotiline	Possible risk for TdP
Melperone (not available in the US)	Possible risk for TdP
Mianserin (not available in the US)	Possible risk for TdP
Midostaurin	Possible risk for TdP
Mifepristone	Possible risk for TdP
Mirabegron	Possible risk for TdP
Mirtazapine	Possible risk for TdP
Necitumumab	Possible risk for TdP
Nicardipine	Possible risk for TdP
Nilotinib	Possible risk for TdP
Norfloxacin	Possible risk for TdP
Nortriptyline	Possible risk for TdP
Nusinersen	Possible risk for TdP
Ofloxacin	Possible risk for TdP
Oliceridine	Possible risk for TdP
Osilodrostat	Possible risk for TdP
Osinotrostat	Possible risk for TdP
Oxytocin	Possible risk for TdP
Ozanimod	Possible risk for TdP
Paliperidone	Possible risk for TdP
Palonosetron	Possible risk for TdP
ו מוטווטזכנו טוו	FUSSINIE HSK IUI TUF

Drug	QT risk (*)
Panobinostat	Possible risk for TdP
Pasireotide	Possible risk for TdP
Pazopanib	Possible risk for TdP
Perflutren lipid microspheres	Possible risk for TdP
Perphenazine	Possible risk for TdP
Pilsicainide (not available in the US)	Possible risk for TdP
Pimavanserin	Possible risk for TdP
Pipamperone (not available in the US)	Possible risk for TdP
Pilsicainide (not available in the US)	Possible risk for TdP
Pitolisant	Possible risk for TdP
Ponesimod	Possible risk for TdP
Pretomanid	Possible risk for TdP
Primaquine phosphate	Possible risk for TdP
Promethazine	Possible risk for TdP
Prothipendyl (not available in the US)	Possible risk for TdP
Relugolix	Possible risk for TdP
Remimazolam	Possible risk for TdP
Ribociclib	Possible risk for TdP
Rilpivirine	Possible risk for TdP
Romidepsin	Possible risk for TdP
Rucaparib	Possible risk for TdP
Saquinavir	Possible risk for TdP
Selpercatinib	Possible risk for TdP
Siponimod	Possible risk for TdP
Sorafenib	Possible risk for TdP
Sunitinib	Possible risk for TdP
Tacrolismus	Possible risk for TdP
Tamoxifen	Possible risk for TdP
Tazemetostat	Possible risk for TdP
Telavancin	Possible risk for TdP
Telithromycin	Possible risk for TdP
Tetrabenazine	Possible risk for TdP
Tiapride (not available in the US)	Possible risk for TdP
Tipiracil and Trifluridine	Possible risk for TdP
Tizanidine	Possible risk for TdP
Tolterodine	Possible risk for TdP
Toremifene	Possible risk for TdP
Tramadol	Possible risk for TdP
Trimipramine	Possible risk for TdP
Tropisetron (not available in the US)	Possible risk for TdP
Valbenazine	Possible risk for TdP
Vardenafil	Possible risk for TdP
Vemurafenib	Possible risk for TdP
Venlafaxine	Possible risk for TdP
Voclosporin	Possible risk for TdP
Vorinostat	Possible risk for TdP
Zotepine (not available in the US)	Possible risk for TdP
Zuclopenthixol, Zuclopentixol (not available in the US)	Possible risk for TdP

Drug QT	T risk (*)
---------	------------

Source:

(\*) Classification according to the Qtdrugs org advisory board of the Arizona CET. Updated versions of medications which may prolong the QTc interval may be found at the following website: https://crediblemeds.org/index.php/?cID=328

